11.1.2 Analysis Method of Primary Effectiveness

All primary effectiveness endpoints will be descriptively statistically summarized.

The percentage of eyes with BCDVA equal to or better than 0.3 logMAR will be used as a categorical variable for summary: 0.0 LogMAR and better, 0.1 LogMAR and better, 0.2 LogMAR and better, and 0.3 LogMAR and better, lower than 0.3 LogMAR, including counts and percentages.

Monocular BCDVA, DCIVA and DCNVA are presented by the first eye, the second eye and all implanted eyes; binocular BCDVA, DCIVA and DCNVA are presented by subject, including sample size, mean,

Version 1.0, Aug 27, 2021 11 / 17

This document is copyrighted by Kun Tuo Medical Research and Development (Beijing) Co., Ltd., and unauthorized use, disclosure or reproduction in any form is prohibited.

median, standard deviation, maximum and minimum, and two-sided 95% confidence interval and categorical analysis. If necessary, provide a listing of the test results.

11.2 Safety Analysis

11.2.1 Primary Safety Endpoint

The primary safety endpoints of this study are as follows, mainly assessing the safety performance at 6 and 12 months after surgery:

Incidence of ocular adverse events, incidence of secondary surgery, and incidence of severe and most bothersome visual disturbances as reported by the subjects using a questionnaire (QUVID).

Version 1.0, Aug 27, 2021 12 / 17

[figure not shown]

11.2.2 Primary Safety Analysis Method

There is no safety hypotheses planned in this study. The focus of safety analysis is to conduct a comprehensive descriptive assessment of adverse events and other listed parameters in the safety analysis set, and list them if necessary.

All AEs occurring from the time a subject signs informed consent to study exit will be accounted for in the reporting. Subjects who have had AEs after signing the informed consent form and before exposure to IP will be displayed in the form of a list; the AEs after exposure to IP (TEAE, treatment emergent adverse event) will be summarized as follows:

- 1. All adverse events (combined serious and non-serious) form
 - a Ocular
 - b. Non-ocular

Protocol number: ILH297-C004 Statistical Analysis Plan

A listing of SSIs will be presented. The listing wage, sex, surgery eye, eye, days from surgery, r Descriptive summaries (counts and percentages	will include all SSI data with the following variables: subjet relationship, and description.	eyes, second implanted eyes and for all eyes combined A listing of SSIs will be presented. The listing will include all SSI data with the following variables: subjective, sex, surgery eye, eye, days from surgery, relationship, and description. Descriptive summaries (counts and percentages) for rates of severe and most bothersome (separately) visit	age, sex, surgery eye, eye, days from surgery, relationship, and description. Descriptive summaries (counts and percentages) for rates of severe and most bothersome (separately) vist	A listing of SSIs will be presented. The listing will include all SSI data with the following variables: subjet age, sex, surgery eye, eye, days from surgery, relationship, and description. Descriptive summaries (counts and percentages) for rates of severe and most bothersome (separately) visit	
A listing of SSIs will be presented. The listing wage, sex, surgery eye, eye, days from surgery, r Descriptive summaries (counts and percentages	will include all SSI data with the following variables: subjetelationship, and description. es) for rates of severe and most bothersome (separately) visu	eyes, second implanted eyes and for all eyes combined A listing of SSIs will be presented. The listing will include all SSI data with the following variables: subjecting eyes, eyes, eyes, days from surgery, relationship, and description. Descriptive summaries (counts and percentages) for rates of severe and most bothersome (separately) visually	A listing of SSIs will be presented. The listing will include all SSI data with the following variables: subjective summaries (counts and percentages) for rates of severe and most bothersome (separately) visus	A listing of SSIs will be presented. The listing will include all SSI data with the following variables: subjet age, sex, surgery eye, eye, days from surgery, relationship, and description. Descriptive summaries (counts and percentages) for rates of severe and most bothersome (separately) visually.	The number and percentage of secondary surgical interventions (SSIs) will be presented for first implant
age, sex, surgery eye, eye, days from surgery, r Descriptive summaries (counts and percentages	relationship, and description. s) for rates of severe and most bothersome (separately) visu	age, sex, surgery eye, eye, days from surgery, relationship, and description. Descriptive summaries (counts and percentages) for rates of severe and most bothersome (separately) visu	age, sex, surgery eye, eye, days from surgery, relationship, and description. Descriptive summaries (counts and percentages) for rates of severe and most bothersome (separately) visu	age, sex, surgery eye, eye, days from surgery, relationship, and description. Descriptive summaries (counts and percentages) for rates of severe and most bothersome (separately) visu	
age, sex, surgery eye Descriptive summar	e, eye, days from surgery, ies (counts and percentage	age, sex, surgery ey Descriptive summar	age, sex, surgery eye Descriptive summar	age, sex, surgery eye Descriptive summar	
e, days from surgery, r counts and percentages	relationship, and description. s) for rates of severe and most bothersome (separately) visual	e, days from surgery, relationship, and description. counts and percentages) for rates of severe and most bothersome (separately) visu	e, days from surgery, relationship, and description. counts and percentages) for rates of severe and most bothersome (separately) visua	e, days from surgery, relationship, and description. counts and percentages) for rates of severe and most bothersome (separately) visus	
age, sex, surgery eye, eye, days from surgery, r Descriptive summaries (counts and percentages	relationship, and description. s) for rates of severe and most bothersome (separately) visua	age, sex, surgery eye, eye, days from surgery, relationship, and description. Descriptive summaries (counts and percentages) for rates of severe and most bothersome (separately) visua	A listing of SSIs will be presented. The listing will include all SSI data with the following variables: subject age, sex, surgery eye, eye, days from surgery, relationship, and description. Descriptive summaries (counts and percentages) for rates of severe and most bothersome (separately) visus disturbances as reported by the subjects using the QUVID questionnaire will be presented per user manual disturbances.	age, sex, surgery eye, eye, days from surgery, relationship, and description. Descriptive summaries (counts and percentages) for rates of severe and most bothersome (separately) visus	
age, sex, surgery eye, eye, days from surgery, r Descriptive summaries (counts and percentages	relationship, and description. s) for rates of severe and most bothersome (separately) visua	age, sex, surgery eye, eye, days from surgery, relationship, and description. Descriptive summaries (counts and percentages) for rates of severe and most bothersome (separately) visua	age, sex, surgery eye, eye, days from surgery, relationship, and description. Descriptive summaries (counts and percentages) for rates of severe and most bothersome (separately) visual	age, sex, surgery eye, eye, days from surgery, relationship, and description. Descriptive summaries (counts and percentages) for rates of severe and most bothersome (separately) visus	
age, sex, surgery eye, eye, days from surgery, r Descriptive summaries (counts and percentages	relationship, and description. s) for rates of severe and most bothersome (separately) visua	age, sex, surgery eye, eye, days from surgery, relationship, and description. Descriptive summaries (counts and percentages) for rates of severe and most bothersome (separately) visua	age, sex, surgery eye, eye, days from surgery, relationship, and description. Descriptive summaries (counts and percentages) for rates of severe and most bothersome (separately) visual	age, sex, surgery eye, eye, days from surgery, relationship, and description. Descriptive summaries (counts and percentages) for rates of severe and most bothersome (separately) visus	
Descriptive summaries (counts and percentages	es) for rates of severe and most bothersome (separately) visua	Descriptive summaries (counts and percentages) for rates of severe and most bothersome (separately) visu	Descriptive summaries (counts and percentages) for rates of severe and most bothersome (separately) visua	Descriptive summaries (counts and percentages) for rates of severe and most bothersome (separately) visus	
uistinoances as reported by the subjects tising t	the QOVID questionnaire will be presented per user manual	asia oances as reported by the subjects using the QOVID questionnaire will be presented per user manua	unstanoances as reported by the subjects using the QOVID questionmante with be presented per user manual	usitaroantes as reported by the subjects using the QOVID questionnaire with be presented per user mainta	
					disturbances as reported by the subjects using the QUVID questionnaire will be presented per user manu-

Version 1.0, Aug 27, 2021 14/17

Protocol number: ILH297-C004

Statistical Analysis Plan

Appendix 2. Specifications for Incomplete Dates

The filled date is not displayed in the list.

Algorithm of adverse events during treatment

Start Date	End Date	Action
Found	Found	If the start date is < the date of investigational IOL implantation, it will
		not be considered as a TEAE
		If the start date is >= the data of investigational IOL implantation, it
		will be considered as a TEAE
	Incomplete	If the start date is < the date of investigational IOL implantation, it will
		not be considered as a TEAE
		If the start date is >= the data of investigational IOL implantation, it
		will be considered as a TEAE
	Loss	If the start date is < the date of investigational IOL implantation, it will
		not be considered as a TEAE
		If the start date is >= the data of investigational IOL implantation, it
		will be considered as a TEAE
Incomplete, but the known part	Found	Non-TEAE
shows that it is unlikely to be the		
same day or later than the start date		
of the investigational drug		N. True
	Incomplete	Non-TEAE
	Loss	Non-TEAE
Incomplete, it may be the same day	Found	If the end date is considered as the date of investigational IOL
or later than the start date of the		implantation, it will not be considered as a TEAE
investigational drug		If the end date is >= the data of investigational IOL implantation, it
		will be considered as a TEAE
	Incomplete	First, fill in the latest possible date as the end date (that is, if the day is
		missing, fill in the last day of the month, if both day and month are
		missing, fill in December 31 of the current year):
		If the end date is considered as the date of investigational IOL
		implantation, it will not be considered as a TEAE
		If the end date is >= the data of investigational IOL implantation, it will be considered as a TEAE
	Loss	Assumed it as a TEAE
	LUSS	Assumed II do d LEAE
1	Found	If the end date is considered as the date of immediational TO
Loss	round	If the end date is considered as the date of investigational IOL implantation, it will not be considered as a TEAE
		If the end date is >= the data of investigational IOL implantation, it
		will be considered as a TEAE
	Incomplete	First, fill in the latest possible date as the end date (that is, if the day is
	ancomplete.	missing, fill in the last day of the month, if both day and month are
		missing, fill in December 31 of the current year):
		If the end date is considered as the date of investigational IOL
		implantation, it will not be considered as a TEAE
		If the end date is >= the data of investigational IOL implantation, it
		will be considered as a TEAE
	Loss	Assumed it as a TEAE

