6.0 General Considerations

6.1 Reference Start Date and Number of Study Days

The number of study days will be calculated from the reference start date and be used to indicate the number of start/end days of the assessment and event.

The reference start date is defined as the date of the first treatment of the investigational device (that is, the day of surgery is Day 0), and will appear in the list of all assessment/event dates.

- If the event date is not earlier than the reference date:
 - Number of study days = (event date reference date) + 1
- If the event date is earlier than the reference date:

Number of study days = (event date-reference date)

If the event date is incomplete or missing, the date in the list will remain incomplete or missing, and the number of study days and any corresponding duration will be presented based on the filling method specified in Annex II (Specifications for Incomplete Dates).

Version 1.0, Aug 27, 2021 8 / 17

Protocol number: ILH297-C004 Statistical Analysis Plan

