6.2 Baseline

The baseline is defined as the last non-missing measurement (including unscheduled measurements) taken before the reference start date. Adverse events and device deficiency on the reference start date will be considered post-baseline.

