6.4 Appointment of visit windows

According to protocol version 2.0, the following table describes the visit window for this study.

Visit	EYE	Day
Visit 0 Pre-Op	Both eyes	Day -28-0
Visit 00 OP ¹	1st Eye	Surgery
Visit 1	1st Eye	Day 1-2
Visit 2	1st Eye	Day 7-14
Visit 00A OP ²	2nd Eye	Surgery
Visit 1A	2nd Eye	Day 1-2
Visit 2A	2nd Eye	Day 7-14
Visit 3A	Both eyes	Day 30-60(Post second eye implant)
Visit 4 A	Both eyes	Day 90-120(Post second eye implant)
Visit 5A	Both eyes	Day 180-210(Post second eye implant)
Visit 6A	Both eyes	Day 360-390(Post second eye implant)
Early Withdrawal	N/A	N/A

- Visit 00 (1st eye surgery) must occur within 28 calendar days from Pre-operative Visit (Visit 0).
- Visit 00A (2nd eye surgery) must be performed within 7 to 28 calendar days after Visit 00 (1st eye surgery).

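### SAP Appendix 2: in four cells of the treatment-emergent AE table, an end date on the implantation day meets both opposite branches and an earlier end date meets neither

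*SAP*

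**What the plan says.** SAP 11.2.2 divides adverse events by exposure to the study lens. Those before exposure are only listed, and those after exposure (TEAEs) are summarised. SAP 11.2.1 makes the ocular AE rate a primary safety endpoint. For incomplete or missing event dates SAP 6.1 refers to Appendix 2, whose table classifies each event by the state of its start date and its end date.

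Where the start date is complete, the non-TEAE branch reads "If the start date is < the date of investigational IOL implantation, it will" not count as a TEAE, and the other branch uses >=. Where the start date is missing, or incomplete but possibly on or after implantation, the table turns to the end date, again with two branches:

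- The branch that leaves the event out of the TEAEs begins "If the end date is considered as the date of investigational IOL" and goes on to name implantation.
- The opposite branch, which makes the event a TEAE, uses a comparison sign: "If the end date is >= the data of investigational IOL implantation, it" counts as one.

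SAP 6.2 adds: "Adverse events and device deficiency on the reference start date will be considered post-baseline". SAP 6.1 fixes that date: "The reference start date is defined as the date of the first treatment of the investigational device".

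**The concern.** The two branches of a classification rule should not overlap and should cover every case. In these cells they do neither. The first branch is evidently meant to catch events that were over before the lens went in, yet its wording catches only events that ended on the day of implantation, and the second branch claims those too. An event that clearly ended before implantation, the easiest case to decide, has no rule.

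Such events can arise. AE collection starts at informed consent (Protocol XIII (III)), and the first surgery may follow the preoperative visit by up to 28 days (SAP 6.4). What is at stake is whether the event enters the summary tables or only the listing of pre-exposure events.

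**Working it through.** No figure in the plan depends on this rule, so the check is one of logic.

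**Step 1: count the cells.** Four start-date states times three end-date states give 4 × 3 = 12 cells.

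| Start date | Cells | Rule |
|---|---|---|
| Complete | 3 | start < implantation: not TEAE; start >= implantation: TEAE |
| Incomplete, known part points to before implantation | 3 | always not TEAE |
| Incomplete, possibly on or after implantation; end date complete or partial | 2 | the faulty pair |
| Same; end date missing | 1 | assumed TEAE |
| Missing; end date complete or partial | 2 | the faulty pair |
| Missing; end date missing | 1 | assumed TEAE |

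The faulty pair fills 2 + 2 = 4 of the 12 cells.

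**Step 2: truth table.** Let d be the end date minus the implantation date, in days. As written, the non-TEAE branch is true when d = 0 and the TEAE branch when d >= 0. The last column puts d < 0 in the first branch.

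| d | Not TEAE (d = 0) | TEAE (d >= 0) | As written | With d < 0 in the first branch |
|---|---|---|---|---|
| −7 | false | false | neither | not TEAE |
| −1 | false | false | neither | not TEAE |
| 0 | true | true | both | TEAE |
| +1 | false | true | TEAE | TEAE |
| +7 | false | true | TEAE | TEAE |

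With the strict inequality every end date falls in exactly one branch.

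**Step 3: partial end dates.** In two of the four cells the end date is first filled with the latest possible day, meaning month end or 31 December. The filled date then equals the implantation date only if surgery fell on that day, so the overlap is rare there. The gap remains whenever the filled date precedes implantation.

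**Step 4: could this be a PDF-reading fault?** Unlikely. The < sign is intact in the complete-start-date rows of the same table, and the faulty phrase appears in full words in all four cells. It looks like a translation or editing slip.

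**Step 5: which repair agrees with the rest of the SAP?** SAP 6.2 treats AEs on the reference date as post-baseline, so a same-day event belongs with the TEAEs. The complete-start-date rows also put the implantation day on the TEAE side. Both support < in the first branch and >= in the second.

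**Step 6: which implantation date?** The appendix names no eye. SAP 6.4 says "Visit 00A (2nd eye surgery) must be performed within 7 to 28 calendar days after Visit 00 (1st eye surgery"). An ocular AE in the second eye between the surgeries is treatment-emergent by the first-eye date and not by that eye's own date. The two readings disagree on 7 days when the gap is 7 days and on 28 days when it is 28. The Safety Set also admits subjects whose lens touched the eye but was not implanted (SAP 5.1). They may have no implantation date at all.

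**The case against.** The strongest reply is that the intended meaning is obvious. The body text separates events before and after exposure, SAP 6.2 settles the same-day case, and the complete-start-date rows show the pattern. The appendix has other slips, such as a reference to an investigational drug in a device study. The study is descriptive with no hypotheses, and pre-exposure events are to be listed, so few reported figures should move. All of this stands and limits the weight of the point. It does not remove it: the SAP replaces the protocol's statistical section, and a pre-specified rule should be programmable without guessing.

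A reader might go further and infer that one implantation date is applied to both eyes, so that second-eye events before that eye's surgery are charged to the lens. The documents do not support this. Appendix 2 names no eye, and the reference start date in SAP 6.1 is a separate term that the appendix does not use. A subject-level flag from first exposure is defensible and fits the wording of SAP 11.2.2. The flag does not assign cause either: causality is judged for every AE (Protocol XIII (IV)), and device- or surgery-related events have their own table (Protocol VIII, 2.5). The public text of SAP 11.2.2 is also too broken to exclude an eye-level rule there. What remains is that the date is not specified in the text available.

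**Conclusion.** The defect holds exactly for four of the 12 cells: both branches are met when the end date is the implantation day, and neither when it is earlier. Events with a later end date are classified correctly.

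The reach is narrow. Only AEs with a missing or ambiguous start date that ended on or before implantation are affected. It would be too broad to include every incomplete start date, because those whose known part points to before implantation are already fixed as not TEAE.

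The number is probably small, and the documents give no rate from which to estimate it. A reader might apply the 1.8% in SAP 3.2 (0.018 × 142 = 2.6 subjects) and infer that one misflagged event would shift the count by a third to a half. That rate is for ocular serious events, whereas the endpoint counts all ocular AEs, for which no planning rate is given.

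The conclusion assumes that the phrase was read correctly from the PDF. The question of which eye's date applies is a secondary clarification and not a second error.

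**What to change.** In the four cells, replace the words *considered as* in the first branch with the sign <. An end date before implantation is then not TEAE, and an end date on or after it is TEAE. While there, correct the references to an investigational drug.

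As a clarification, add a sentence saying which date the appendix means. One option is the subject's first exposure to the study lens, including lens contact without implantation. Add another saying how eye-level tables treat second-eye events between the two surgeries. A rule based only on the affected eye's own date would need a fallback, because Protocol Table 7-6 allows subjects to continue with an eye that never received or touched a study lens.

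The cost is a few words in the SAP and a small change to the derivation code, made before database lock. No new data are needed.
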